7 BLINDING

This is an open-label study. Participants and site staff will be unblinded to participants' group assignments. Laboratory program staff will be blinded to participants' group assignments during assay analysis, whenever feasible.

8 SAMPLE SIZE

The goal of the safety evaluation for this study is to identify safety concerns associated with vaccine administration. The ability of the study to detect SAEs (see Section 9.2 of protocol) can be expressed by the true event rate above which at least 1 SAE would likely be observed and the true event rate below which no events would likely be observed. Specifically, for each treatment group of size n = 18 (Groups 2 or 3), there is at least a 90% chance of observing at least 1 event if the true rate of such an event is 12.5% or more, and there is at least a 90% chance of observing no events if the true rate is 0.53% or less. When pooling Groups 2 and 3 together (n = 36), there is at least a 90% chance of observing at least 1 event if the true rate of such an event is 6.5% or more, and there is at least a 90% chance of observing no events if the true rate is 0.29% or less. Safety data will be summarized as described in Section 6.4.3 of the protocol and evaluated using historical controls. As a reference, in HVTN vaccine trials conducted in the US from April 2008 through March 2018, about 1% of participants who received placebos experienced an SAE.

Binomial probabilities of observing 0 events, 1 or more events, and 2 or more events among 9 (or 18 or 36 or 45) participants receiving the study vaccine are presented in Table 8-1 for a range of possible true AE rates. These calculations provide a more complete picture of the sensitivity of this study design to identify potential safety problems with the vaccine.

Table 8-1 Probability of observing 0 events, 1 or more events, and 2 or more events among a group of 9, 18, 36, or 45 study participants for different true event rates

True event rate (%)	Arm size	0 events	1+ events	2+ events
1	9	0.91	0.09	0.00
4	9	0.69	0.31	0.05
10	9	0.39	0.61	0.23
20	9	0.13	0.87	0.56
30	9	0.04	0.96	0.80
1	18	0.83	0.17	0.01
4	18	0.48	0.52	0.16
10	18	0.15	0.85	0.55
20	18	0.02	0.98	0.90
30	18	0.00	1.00	0.99
1	36	0.70	0.30	0.05
4	36	0.23	0.77	0.42
10	36	0.02	0.98	0.89
20	36	0.00	1.00	1.00
30	36	0.00	1.00	1.00
1	45	0.64	0.36	0.07
4	45	0.16	0.84	0.54
10	45	0.01	0.99	0.95
20	45	0.00	1.00	1.00
30	45	0.00	1.00	1.00

An alternative way of describing the statistical properties of the study design is in terms of the 95% CI for the true rate of an AE based on the observed data. Table 8-2 shows the two-sided 95% CIs for the probability of an event based on a particular observed rate. Calculations are done using the score test method for CIs described in Agresti and Coull formula 2 (53). If none of the 18 participants receiving the study vaccine in Groups 2 or 3 experience a safety event, the 95% two-sided upper confidence bound for the true rate of such events in the total vaccinated population is 17.6%. Table 8-2 also includes CIs for groups of size n = 9 (Group 1 alone), n = 36 (Groups 2 and 3 pooled together), and n = 45 (all 3 treatment groups combined).

Table 8-2 Two-sided 95% CIs for the probability of observing a safety event based on observing a particular rate of safety endpoints in a group of 18, 36, or 54 study participants

Observed event rate	95% CI (%)
0/9	[0;29.9]
1/9	[2.0; 43.5]
2/9	[6.3;54.7]
0/18	[0; 17.6]
1/18	[1.0; 25.8]
2/18	[3.1; 32.8]
0/36	[0; 9.6]
1/36	[0.5; 14.2]
2/36	[1.5; 18.1]
0/45	[0;6.6]
1/45	[0.3; 9.8]
2/45	[1.0; 12.5]

9 STATISTICAL ANALYSIS

This section describes the final study analysis, unblinded as to treatment arm assignment. All data from enrolled participants will be analyzed regardless of how many vaccinations they received. All analyses will be performed using SAS and/or R.

9.1 Baseline demographics

Participants' baseline characteristics will be summarized using descriptive statistics.

9.2 Safety Analyses

Reactogenicity: The number and percentage of subjects experiencing each type of reactogenicity sign or symptom will be tabulated by severity. For a given sign or symptom, each subject's reactogenicity will be counted once under the maximum severity for all assessments.

Adverse Events: AEs will be coded into Medical Dictionary for Regulatory Activities (MedDRA) preferred terms. The number and percentage of subjects experiencing each specific AE will be tabulated by severity and relationship to study vaccine. For the calculations in these tables, each subject's AE will be counted once under the maximum severity or strongest recorded causal relationship to treatment. A complete listing of AEs for each subject will provide details including severity, relationship to treatment, onset, duration and outcome.

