8.3 Reactogenicity assessments

Reactogenicity definition: Signs and symptoms considered to represent reactogenicity from the vaccine include systemic events of increased body temperature, fatigue, generalized myalgia, generalized arthralgia, headache, chills, nausea, and local events at the injection site, including pain/tenderness, induration, and erythema.

The reactogenicity assessment period is the day of vaccination and 7 full days following vaccine administration for INO-6172 alone and 14 full days following vaccine administration for INO-6172 along with Trimer 4571 adjuvanted with 3M-052-AF/Alum and Trimer 4571 alone, adjuvanted with 3M-052-AF/Alum. Clinicians will follow and collect resolution information for any reactogenicity signs and symptoms that have not resolved within the reactogenicity assessment period.

Prevaccine administration: Medical history and evaluations, including vital signs and planned injection-site evaluations, are performed as described in Appendix A and Appendix B

Postvaccine administration in-clinic evaluation: Following the first vaccine administration of sD-NP-GT8, participants will be observed for a minimum of 60 minutes postadministration. For all subsequent injections, participants will be observed for a minimum of 30 minutes with the following exception: for Group 3, participants will be observed for 60 minutes postadministration of Trimer 4571 + 3M-052-AF + Alum. During this time, vital signs will be recorded, the injection site will be inspected for evidence of local reaction, and any evidence of systemic symptoms will be assessed.

Postvaccine administration contact with participant: Remote or in-person contact between the participant and the site staff should take place at least once on the third or fourth day following vaccination. Any postvaccination reaction that is Grade 2 or higher will be assessed by a clinician within 48 hours after onset unless the reaction is improving and/or has completely resolved. Additionally, other clinical concerns may prompt a study visit based on the judgment of a study clinician.

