Guidance for participants scheduling licensed vaccines or allergy treatments: In order to prevent interference with reactogenicity assessments, participants who plan to receive licensed vaccines or allergy treatments should be counseled to avoid scheduling receipt of these substances, when possible, within the 2 week interval after study product administration. To avoid unnecessary delays in study product administration, participants should be counseled to avoid scheduling receipt of these substances before study product administration (see Section 5.2.1).

Symptom diaries: Participants are asked to record symptoms on a daily basis using an electronic participant diary (paper alternative is available). All participants will be given a thermometer for oral temperature measurement and a ruler, and will be provided access to the electronic diary (paper alternative available). All participants will be provided training on diary completion, proper thermometer usage, and how to use of the measuring device to measure any injection-site induration and/or erythema. Participants will use the diary to record daily their highest temperature as well as local and systemic signs and symptoms. For Groups 1 and 2, symptoms are recorded for the day of vaccination and for 7 full days following each vaccination. For Group 3 only, symptoms are recorded for the day of vaccination, for 7 full days following the first two vaccinations, and for 14 full days following the third and fourth vaccinations. Participant diaries will be reviewed by a clinician and reconciled for accuracy and completeness. Attribution assessment will be performed and recorded on a case report form (CRF) for systemic reactogenicity events reported in the participant diary after additional evaluation of the participant by clinician. Clinicians may photograph the injection site in order to document injection-site reactogenicity.

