10 SAFETY TABLES, PARTICIPANT LISTINGS, AND FIGURES

10.1 List of Tables

- Enrollment Report
- Demographics and Vaccination Frequencies
- Overall Protocol Status
- Maximum Local and Systemic Reactogenicity Summaries
- Adverse Experiences by Body System and Severity By Decreasing Frequency
- Adverse Experiences by Preferred Term and Severity By Decreasing Frequency Includes Severe, Life-threatening or Fatal Experiences Only
- Adverse Experiences by Preferred Term and Severity By Decreasing Frequency Includes Experiences of All Severities
- Adverse Experiences by Preferred Term and Relationship to Study Product By Decreasing Frequency – Includes Related Experiences Only
- Expedited Adverse Experiences (EAEs) Reported to the Regulatory Support Center (RSC)
- Medically Attended Adverse Events (MAAE)
- Pre-Enrollment Procedure-Related Events
- Pregnancy Listing

Additional tables included in the FSR for Safety:

- Social Impact Summary
- End of Study Diagnostic ELISA Testing Results
- Local Lab Value Summary Statistics
- Local Laboratory Values Meeting Grade 1 AE Criteria or Above

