10.2 List of Participant Listings

These participant listings are included in the SMB reports:

- Discontinuation Status
- Pregnancies
- Severe or Life-Threatening Local and Systemic Reactogenicities
- Moderate Erythema and Induration
- Expedited Adverse Experiences (EAEs)
- Adverse Experiences of Special Interest (AESIs)
- Severe, Life-Threatening, or Fatal Adverse Experiences
- Adverse Experiences with Relationship to Study Product

- HIV Infection Results from Lab and Reported by Site
- Study Product Administration Errors
- Device Related Adverse Events

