10.3 List of Figures

These graphs are included in the SMB reports and FSR for Safety:

- Maximum Local Reactogenicities
- Maximum Systemic Reactogenicities
- Boxplots for ALT, Creatinine, Hemoglobin, Platelet Count, AST, WBC, Neutrophil Count, Lymphocyte Count, Monocytes, Eosinophils, Basophils, Atypical lymphocytes

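### Reactogenicity is summarised only as one maximum per participant over the whole regimen; adding tables by vaccination visit and product, with Groups 2 and 3 pooled for doses 1 and 2, is a cheap improvement.

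*SAP*

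**What the plan says.** Reactogenicity is endpoint (a) of primary objective 1. For each sign or symptom, SAP 9.2 says "each subject's reactogenicity will be counted once under the maximum severity for all assessments"; protocol 6.4.3 has the same rule. The only reactogenicity table named in SAP 10.1 is "Maximum Local and Systemic Reactogenicity Summaries". The figures in SAP 10.3 are the matching local one and "Maximum Systemic Reactogenicities". SAP 10.2 adds two participant listings for the Safety Monitoring Board (SMB) reports: "Severe or Life-Threatening Local and Systemic Reactogenicities" and "Moderate Erythema and Induration".

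Collection is organised by dose and product. Protocol 8.3 sets the assessment period at "7 full days following vaccine administration for INO-6172 alone and 14 full days following vaccine administration for INO-6172 along with Trimer 4571", and the same 14 days when adjuvanted Trimer is given alone. On the diary it says: "For Groups 1 and 2, symptoms are recorded for the day of vaccination and for 7 full days following each vaccination". Group 3 records "for 7 full days following the first two vaccinations, and for 14 full days following the third and fourth vaccinations".

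Protocol 6.1.1 notes that Groups 2 and 3 receive identical products up to Day 85. SAP 8 already quotes safety precision for those two groups pooled at n = 36.

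**The concern.** Group 3 passes through three different exposures: 2 mg DNA alone at doses 1 and 2, DNA with adjuvanted Trimer at dose 3, and adjuvanted Trimer alone at dose 4. Groups 1 and 2 receive DNA alone throughout. One maximum over all assessments merges the three Group 3 exposures into one figure and sets it beside a figure built from fewer visits and fewer diary days.

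For a first-in-human DNA product, the useful tolerability question is which injection a reaction followed. Protocol 2.8 raises, and argues against, a theoretical increase in local reactions when DNA and protein are aimed at the same lymph node. Dose 3 is where the trial's own data bear on that, and the overall maximum blends dose 3 with doses 1, 2 and 4.

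**Working it through.** **1. What the maximum spans** (protocol 8.3 diary rules; vaccination day counted as one day)

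- Groups 1 and 2: 3 visits, 3 × (1 + 7) = 24 diary days, all after DNA alone.
- Group 3: 4 visits, 2 × (1 + 7) + 2 × (1 + 14) = 16 + 30 = 46 diary days. Of these, 16 follow DNA alone, 15 follow DNA with Trimer and 15 follow Trimer alone.
- The endpoint table (protocol 3.1, SAP 3.1) instead gives a minimum of 2 weeks after any vaccine. On that text the totals are 3 × 15 = 45 and 4 × 15 = 60.
- The ratio is therefore 46/24 = 1.92 or 60/45 = 1.33, depending on which text governs. The difference of 4 visits against 3 holds either way.

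**2. What the listings recover**

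Protocol 8.3 names 7 systemic and 3 local items, 10 in all. Severe or life-threatening reactions are listed for all 10, and moderate reactions for erythema and induration only. For the other 8 (pain/tenderness and the 7 systemic symptoms), no reactogenicity listing covers anything below severe.

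**3. Gap produced by the extra visit alone**

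Assumption, not in the documents: every visit carries the same reaction rate p in both groups. With independent visits, the share of participants with at least one reaction is 1 − (1 − p)^k for k visits, and the gap is p(1 − p)³.

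| p per visit | 3 visits | 4 visits | Gap (points) |
|---|---|---|---|
| 5% | 14.3% | 18.5% | 4.3 |
| 10% | 27.1% | 34.4% | 7.3 |
| 20% | 48.8% | 59.0% | 10.2 |
| 30% | 65.7% | 76.0% | 10.3 |

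The gap peaks at p = 25%: 0.25 × 0.75³ = 10.5 points. If instead the same people react at every visit, the gap is 0. The range is 0 to about 10 points, depending on within-person dependence.

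**4. Attribution**

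With independent visits, a DNA-visit rate of 10% and a Trimer-visit rate of 20% give a Group 3 maximum of 1 − 0.9² × 0.8² = 48.2%. Exchanging the two rates gives 1 − 0.8² × 0.9² = 48.2% again. Group 2's maximum would differ (27.1% against 48.8%), so it gives indirect information about DNA. Nothing separates dose 3 from dose 4.

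**5. Pooling doses 1 and 2**

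The upper limit of the score interval for 0 of n is z²/(n + z²), with z² = 3.84.

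- n = 18: 3.84/21.84 = 17.6%.
- n = 36: 3.84/39.84 = 9.6%.

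Both reproduce SAP Table 8-2. For a common reaction, seen in one third of participants, the 95% interval narrows from 16.3–56.3% (6/18) to 20.2–49.7% (12/36).

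**The case against.** - **The regimen maximum fits the objective.** Primary objective 1 concerns three DNA doses with or without two Trimer doses, which is a regimen-level question, and no between-group safety test is planned. This stands. A reader might infer that the planned table is wrong; the documents do not support that.
- **The table shells are not shown.** SAP 9.2 does not even mention treatment-group columns, so it is not a full table specification, and the shells may already split by visit. That is possible. The point rests on the written rule and the titles; if the shells do split, a sentence in SAP 9.2 settles it.
- **The data exist by dose.** Diaries are kept after each vaccination, and attribution of systemic reactions goes on a case report form. A reader might infer that milder reactions can never be placed by dose. That goes too far: what is missing is a specified output. SAP 9.2 also promises a complete adverse event listing with onset, but treats reactogenicity separately and does not say that milder reactions enter that listing.
- **Diary days overstate the imbalance.** A reader might take 46 against 24 days as nearly twice the chance of a reaction. The endpoint text gives 60 against 45, and reactions cluster early: protocol 2.4 reports that those with BG505 SOSIP.664 and 3M-052-AF generally resolved within 7 days.
- **Historical controls.** A reader might take SAP 8's reference to historical controls as a commitment to dose-by-dose comparison with earlier trials. That passage concerns detection of serious adverse events, and its only reference figure is a placebo rate of about 1%.

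**Conclusion.** The point holds as a cheap improvement to a valid plan. Followed as written, the SAP gives no reactogenicity summary by dose or product. Its listings leave pain/tenderness and the seven systemic symptoms unplaced below severe grade. In Group 3 that obscures which of three exposures a mild or moderate reaction followed, on a primary safety endpoint.

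The consequence is loss of description; no test or decision rule is affected. The artificial gap of 0 to about 10 points assumes equal per-visit rates and is not an estimate for this trial. The gain from pooling rests on the planned 18 + 18 participants and on identical exposure at doses 1 and 2.

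**What to change.** Keep the overall maximum as the regimen-level table. Add to SAP 9.2 and to the lists in SAP 10:

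- **(a)** Maximum reactogenicity by treatment group and vaccination visit, labelled by product received: DNA 0.5 mg doses 1–3; DNA 2 mg doses 1–2; DNA 2 mg dose 3; DNA 2 mg with adjuvanted Trimer dose 3; adjuvanted Trimer alone dose 4. The denominator is participants who received that dose.
- **(b)** Groups 2 and 3 combined (planned n = 36) for doses 1 and 2 only.
- **(c)** A common day 0–7 window wherever groups are shown side by side, giving 8 diary days per dose in every group. Show days 8–14 after Group 3 doses 3 and 4 separately.

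This is a change to text and table shells and needs no new data. SAP 1 provides for an update before the first SMB report and again before the final analysis. The documents do not show whether the first of these has passed, but either would serve. The downside is more descriptive tables, with small cells (n = 9 or 18) outside the pooled columns.

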5.2.4 Discontinuation of study participation

A participant may be discontinued from protocol participation for the following reasons:

- Participant voluntarily withdraws;
- CRS determines the participant is lost to follow-up;
- The investigational new drug (IND) application sponsor or regulatory authorities stop the study; or,
- PI assessment that it is not in the best interest of the participant to continue participation in the study or that the participant's compliance with the study is not sufficient.

If a participant terminates participation in the study early for any reason, the site PI should consider if the following assessments are appropriate: end-of-study HIV test, complete blood count (CBC with differential, serum chemistry [ALT and creatinine], physical examination, and if indicated, a pregnancy test [see Appendix A and Appendix B]). For participants living with HIV, please see

Section 8.8. If the site PI has questions regarding a termination visit, they should consult with the PSRT.

6 Statistical considerations

This phase-1 study will target recruiting a total of 45 adult participants without HIV aged 18 to 55 years.

In Group 1, a total of approximately 9 participants will receive 3 administrations of sD-NP-GT8 DNA at a dose of 0.4 mg, coformulated with IL-12 DNA at a dose of 0.1 mg at days 1, 29, and 85. Study products will be administered intradermally via EP of the skin on each upper arm.

In Group 2, a total of approximately 18 participants will receive 3 administrations of sD-NP-GT8 DNA at a dose of 1.6 mg, coformulated with IL-12 DNA at a dose of 0.4 mg at days 1, 29, and 85. Study products will be administered intradermally via EP of the skin on each upper arm.

In Group 3, a total of approximately 18 participants will receive 3 administrations of sD-NP-GT8 DNA at a dose of 1.6 mg, coformulated with IL-12 DNA at a dose of 0.4 mg at days 1, 29, and 85. These doses will be administered intradermally via EP of the skin on each upper arm. All participants in Group 3 will also receive 2 administrations of Trimer 4571 at a dose of 100 mcg adjuvanted with 5 mcg of 3M-052-AF + 500 mcg Alum via IM injections into the deltoid muscle at days 85 and 169.

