9.1 AEs

AEs will be collected over a period of 30 days after each vaccination. All collected AEs are captured in the clinical database on the appropriate CRF. Clinic staff should evaluate every AE to determine if (1) the AE meets the requirements for expedited reporting (see Section 9.2.1), (2) the AE meets the criteria for a safety pause/prompt AE review (see Section 9.6), (3) the AE meets the criteria for an MAAE, and (4) the AE is a potential immune-mediated disease that may be listed as an AESI. A sample list of AESIs is provided in Appendix I.

In addition, a limited set of AEs will be collected and reported until (but not including) the month 18 visit:

- SAEs/expedited adverse events (EAEs),
- AESIs,
- MAAEs, and
- AEs leading to early participant withdrawal or early discontinuation of study vaccine(s) administration.

AEs will be graded according to the DAIDS Table for Grading the Severity of Adult and Pediatric Adverse Events, Corrected Version 2.1 (https://rsc.niaid.nih.gov/clinical-research-sites/daids-adverse-event-grading-tables), with the following exceptions:

- Unintentional weight loss is required to be reported as an AE only if it is considered to be potentially deleterious to the participant's health (see HVTN 305 SSP).
- Do not grade creatinine clearance or estimated glomerular filtration rate (eGFR) based on the change from the baseline parameter. Do not grade on the basis of eGFR if there is clinical concern for acute kidney injury.
- Injection-site erythema or redness and injection-site induration or swelling will not consider surface area and interference with usual social and functional activities, such that:

Grade 1 is: 2.5 to < 5 cm in diameter;

Grade 2 is: > 5 to < 10 cm in diameter;

Grade 3 is: ≥ 10 cm in diameter OR ulceration OR secondary infection OR phlebitis OR sterile abscess OR drainage;

Grade 4 is: potentially life-threatening consequences (eg, abscess, exfoliative dermatitis, necrosis involving dermis or deeper tissue).

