- ¹⁷ Vaccination 4/Visit 10 will be conducted only for participants assigned to Group 3.
- ¹⁸ **AESI contact:** CRS staff will contact study participants at month 18 to collect the information listed in Section 8.10. The EP-injection–site assessment will be an abbreviated questionnaire that can be conducted over phone.

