2.6 Study plan and schema table

Participants will receive INO-6172 (sD-NP-GT8 + IL-12 DNA) vaccinations at months 0, 1, 3, and 6 with a total dose of 0.5 mg (Group 1) or 2 mg (Groups 2 and 3). For Group 1, sD-NP-GT8 DNA will be administered at a dose of 0.4 mg along with IL-12 DNA at a dose of 0.1 mg (0.5 mg total). For Groups 2 and 3, sD-NP-GT8 DNA will be administered at a dose of 1.6 mg along with 0.4 mg of IL-12 DNA (2 mg total). These will be administered intradermally via EP of the skin. Due to volume limitations of the device, the dose of the DNA will be administered as 2 separate intradermal (ID) injections. Each of 2 sites will receive 0.1 mL of study product (either the 1.0-mg/0.1-mL concentration or the 0.25-mg/0.1-mL concentration) via ID injection (Mantoux injection) bilaterally 1 on each upper arm. Following ID injections, EP will be performed with the Inovio CELLECTRA 2000 EP device.

A total of 18 out of 45 participants (Group 3) will also be administered Trimer 4571 at a total dose of 100 mcg at months 3 and 6. The Trimer dose is split over 2 injection sites. The injections are delivered intramuscularly (IM) via needle and syringe, 1 in each deltoid muscle. Participants will be evaluated for safety and immune responses through blood collection, lymph node fine-needle aspiration (FNA), and leukapheresis at specified timepoints throughout the study. The study schema is presented below in Table 2-1:

Table 2-1 Schema

				Inject	ion schedul	e in months	(days)
Group	N	Product/Dose	Route	Month 0 (Day 1)	Month 1 (Day 29)	Month 3 (Day 85)	Month 6 (Day 169)
1**	9	INO-6172 (0.5 mg)	ID EP (2 injections; 1 into skin of each upper arm)	X	X	X	
2§	18	INO-6172 (2 mg)	ID EP (2 injections; 1 into skin of each upper arm)	X	X	X	1
28	18	INO-6172 (2 mg)	ID EP (2 injections; 1 into skin of each upper arm)	X	X	Χ [†]	
3§	18	Trimer 4571 (100 mcg) + 3M-052 AF (5 mcg) / Alum (500 mcg)	IM (2 injections; 1 into each deltoid)	1	ł	\mathbf{X}^{\dagger}	Х
Total	45*						

Notes:

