3 SAFETY OBJECTIVES AND ENDPOINTS

3.1 Primary objectives and endpoints

Objectives	Endpoints
1) To evaluate the safety and tolerability of 3 doses of sD-NP-GT8 + IL-12 DNA adjuvant with or without 2 doses of Trimer 4571 + 3M- 052-AF/Alum adjuvant	a) Local and systemic reactogenicity signs and symptoms will be collected for a minimum of 2 weeks following receipt of any study vaccine
	b) SAEs, medically attended adverse events (MAAEs), AESIs, and AEs leading to early participant withdrawal or permanent discontinuation will be collected throughout the study and for 12 months following any receipt of study products. Additionally, all AEs will be collected for 30 days after any receipt of study vaccination.
2) To evaluate the immunogenicity of 3 doses of sD-NP-GT8 + IL-12 DNA adjuvant with or	a) Response rate and magnitude of HIV-1–specific binding Ab responses to eOD-GT8-60mer, eOD-GT8 monomer, or Trimer 4571 as assessed by multiplex assay 2 weeks following the third (Groups 1 and 2) and fourth (Group 3) vaccinations
without 2 doses of Trimer 4571 + 3M-052-AF/Alum adjuvant	b) Response rate and magnitude of CD4+ and CD8+ T-cell responses, measured by flow cytometry, to HIV-1–specific Env peptide pools 2 weeks following the third (Groups 1 and 2) and fourth (Group 3) vaccinations
3) To evaluate the induction of VRC01-class B cells	a) Frequency of VRC01-class B cells from lymph nodes and periphery following the second and third vaccinations

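### The planned AE percentages ignore that all-AE collection lasts 121 days in Group 3 and 90 days in Groups 1 and 2; by-dose tables and a person-time rate should be added

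*SAP*

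**What the plan says.** **Collection period.** Protocol 9.1: "AEs will be collected over a period of 30 days after each vaccination". The SAP repeats this in endpoint 1b (SAP 3.1): "Additionally, all AEs will be collected for 30 days after any receipt of study vaccination". Protocol 9.1 then lists a limited set that is collected up to the month 18 contact in every group: SAEs/EAEs, AESIs, MAAEs, and AEs leading to withdrawal or to discontinuation of vaccine.

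**Vaccination days.** The opening text of protocol Section 6 gives all three groups the DNA product on Days 1, 29 and 85; for Groups 2 and 3 it is "coformulated with IL-12 DNA at a dose of 0.4 mg at days 1, 29, and 85". Group 3 also receives the Trimer "via IM injections into the deltoid muscle at days 85 and 169". Appendix A, footnote 17, confirms the difference: "Vaccination 4/Visit 10 will be conducted only for participants assigned to Group 3". SAP Table 2-1 shows the same schedule.

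**Summary measure.** SAP 9.2: "The number and percentage of subjects experiencing each specific AE will be tabulated by severity and relationship to study vaccine". Protocol 6.4.3 has the same rule. Each subject's AE is counted once, at its maximum severity or strongest causal relationship. The tables in SAP 10.1 carry titles such as "Adverse Experiences by Body System and Severity By Decreasing Frequency". None is described as by dose, restricted to a common window, or expressed per unit of time. Neither SAP 9.2 nor 10.1 says what the columns are.

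**Two conflicting entries.** The narrative of SAP 2.6 has INO-6172 "vaccinations at months 0, 1, 3, and 6 with a total dose of 0.5 mg (Group 1) or 2 mg (Groups 2 and 3"), which disagrees with Table 2-1 directly below it and with the protocol. The schedules in protocol Appendices A and B also tick AE collection at Visit 11 (Day 183) for all groups.

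**The concern.** A percentage of subjects ever affected rises with the time they are observed. Group 3 has one more 30-day collection window than Groups 1 and 2, so with identical background rates its percentage is expected to be higher.

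Primary objective 1 is the safety of the DNA regimen with or without the Trimer. Group 2 against Group 3 is the randomized contrast at the same DNA dose that isolates the Trimer. A reader who sets those two columns side by side would be comparing percentages gathered over different lengths of time. The same SAP governs the SMB reports (SAP Section 1), so these tables also inform monitoring.

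A single whole-study percentage also merges the DNA-only, DNA-plus-Trimer and Trimer-only periods. For immunogenicity, protocol 6.1.1 recognises that Groups 2 and 3 are the same until Day 85 and allows them to be pooled up to then. The AE summaries have no counterpart.

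**Working it through.** The documents state no number of AE-collection days, so there is no planned figure to reproduce. I use the schedule in protocol Section 6 and SAP Table 2-1.

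**1. Days of all-AE collection at target days.** Each window is taken as [vaccination day, vaccination day + 30], and overlapping days are counted once.

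- Vaccinations 1 and 2: Days 1–31 and 29–59 overlap on Days 29–31, so together they cover Days 1–59 = 59 days.
- Vaccination 3: Days 85–115 = 31 days.
- Groups 1 and 2: 59 + 31 = **90 days**.
- Vaccination 4 (Group 3 only): Days 169–199 = 31 days.
- Group 3: 90 + 31 = **121 days**. Ratio 121/90 = **1.34**.

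**2. Sensitivity to the counting convention.** Leaving out the vaccination day gives 88 and 118 (1.34). Vaccination 2 on Day 38, late enough to remove the overlap, gives 93 and 124 (1.33). Vaccination 2 on Day 57, the latest allowed (29 + 28, Appendix C), gives 90 and 121 again.

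**3. Effect on an ever/never percentage.** Assume a constant background hazard, no vaccine effect and full follow-up. If p is the 90-day proportion, the 121-day proportion is q = 1 − (1 − p)^(121/90). The values of p are assumptions.

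| p over 90 days | q over 121 days | Difference (points) | Extra subjects of 18 |
|---|---|---|---|
| 5% | 6.7% | 1.7 | 0.3 |
| 10% | 13.2% | 3.2 | 0.6 |
| 20% | 25.9% | 5.9 | 1.1 |
| 30% | 38.1% | 8.1 | 1.5 |
| 50% | 60.6% | 10.6 | 1.9 |

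The difference peaks at 10.8 points, at p of about 58%.

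**4. How often the tendency would show.** With two independent binomial groups of 18 and p between 5% and 90%, Group 3 has more affected subjects than Group 2 with probability 0.43 to 0.70, and fewer with probability 0.16 to 0.28. The remainder are ties.

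**5. What the conflicting entries would change.** Read literally, the SAP 2.6 narrative would put a Month 6 vaccination in all groups, and each would then have 121 days. The Visit 11 tick falls 183 − 115 = 68 days after the last Groups 1 and 2 window closes at target days. If AEs were recorded there for all groups, the collection period would differ from protocol 9.1. The windows cannot be fixed until these passages are reconciled.

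**The case against.** Most of the case on the other side limits how far the point reaches.

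- **No between-group safety comparison is planned.** SAP Section 8 evaluates safety against historical controls, and the planned group comparisons concern immunogenicity. This stands: no test is biased. But displayed percentages will still be read across, and a historical comparison of AE percentages also needs a known observation period.
- **The columns are not stated.** This stands. By-group display is an inference, supported by SAP Section 9 describing an analysis unblinded to treatment arm. The silence is itself something to settle.
- **The extra 31 days follow a real dose.** This stands. The proportion with an AE within 30 days of any dose is a legitimate description of a regimen with four vaccination visits. A reader might infer that any Group 3 excess is an artefact of observation time; only its background part is.
- **Events can be placed in time.** This stands. SAP 9.2 plans a listing with onset and relationship, and with 45 participants an event can be assigned to a dose by hand. A reader might infer that an excess could never be located; the listing shows otherwise, though it is not a summary. The table of related AEs reduces the problem without removing it, since site staff know the allocation (protocol 6.3).
- **Participants who stop early stay in the denominator.** SAP Section 9 chooses this openly by analysing everyone regardless of doses received. It is not an oversight, and a person-time rate complements it.

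**Conclusion.** The point holds as a gap in how AEs are summarised. On the protocol schedule, all-AE collection is 90 days in Groups 1 and 2 and 121 days in Group 3, and the planned percentage takes no account of it. If shown by group, the Group 3 percentage is expected to be higher from background events alone. Under a constant hazard and assumed 90-day percentages of 5 to 50%, the excess is 1.7 to 10.6 points, or 0.3 to 1.9 subjects of 18. A specific AE term at 5 to 10% sits at the low end, 0.3 to 0.6 of a subject.

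Two stronger readings are tempting and are not supported. One is that Group 3 will look less safe. The shift is a tendency whose size depends on an AE rate the documents do not give, and chance can reverse it in groups of 18. The other is that all unsolicited AEs are affected. SAEs/EAEs, AESIs, MAAEs and AEs leading to withdrawal or discontinuation are followed towards month 18 in every group, so they do not carry the 121-to-90 imbalance.

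**What to change.** In SAP 9.2 and 10.1, and in protocol 6.4.3:

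1. Keep the overall AE table for the whole regimen and state that its columns are by group.
2. Add AE tables by group for the 30 days after each dose, anchored to each participant's actual vaccination date. Fixed calendar periods would fail: vaccination 2 may fall as late as Day 57, with collection running to Day 87.
3. Assign an event in overlapping windows to the most recent dose. Use the participants who received that dose as the denominator. Groups 2 and 3 may be pooled for doses 1 and 2.
4. Read across groups on the windows after doses 1 to 3. Show the window after dose 4 separately for Group 3, so that it is not dropped. The second Trimer dose then has no concurrent comparator, and the table should say so.
5. Beside the overall table, give AEs per 100 person-days of all-AE collection, counting overlapping days once.
6. Reconcile the schedule text in SAP 2.6 with its Table 2-1 and the protocol, and the Visit 11 AE tick in Appendices A and B with the 30-day rule in protocol 9.1, because these determine the windows.

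The cost is SAP wording, matching protocol text and a few extra tables with smaller cells. Onset dates are already collected, so no visits or participants are added.
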